8.1.5 Safety Analysis

All AEs, SAEs, AEs leading to discontinuation, and pre-specified AESIs will be collected during the study. A treatment-emergent AE (TEAE) is defined as an event with onset or worsening after the first study dose of a risankizumab (either in a preceding Phase 2/3 psoriasis study or this study) and within 20 weeks (140 days) after the last study drug injection. The number and percentages of subjects experiencing TEAE will be tabulated using the Medical Dictionary for Drug Regulatory Activities (MedDRA[®]) system organ class and preferred term. Summaries (including percentages and event per 100 patient-years) of SAEs, deaths, AEs leading to discontinuation from the study, and pre-specified AESIs will be provided as well. Mean change in laboratory and vital signs variables will be summarized. For selected parameters, a listing of all subjects with clinically significant laboratory or vital sign values will be provided. Shift tables for changes from baseline according to the normal range will also be provided.

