The number and percentage of subjects experiencing treatment-emergent adverse events will be summarized for the following adverse event categories:

- Any AE
- Any AE that was assessed as related to study drug by the investigator
- Any severe AE
- Any serious AE
- Any serious AE that was assessed as related to study drug by the investigator
- Any AE leading to discontinuation of study drug
- Any AE leading to death
- Any deaths
- Areas of Safety Interest
- Any COVID-19 Related AE

2. Adverse Events by System Organ Class and Preferred Term

TEAEs will also be summarized and presented using primary Medical Dictionary for Regulatory Activities (MedDRA) system organ classes (SOCs) and preferred terms (PTs). The SOCs will be presented in alphabetical order, and the PTs will be presented in alphabetical order within each SOC.

Subjects reporting more than one adverse event for a given MedDRA preferred term will be counted only once for that term (most severe incident for the severity tables and most related incident for the relationship tables). Subjects reporting more than one type of adverse event within a SOC will be counted only once for that SOC. Subjects reporting more than one type of adverse event will be counted only once in the overall total.

In addition, the number and percentage of adverse events with causal relationship between the events and the study drug will be summarized using the same conventions described above.

3. Adverse Events by Maximum Severity

The severity grading of AEs follows Rheumatology Common Toxicity Criteria (RCTC).

- Grade 1 – mild
- Grade 2 – moderate
- Grade 3 – severe
- Grade 4 – life threatening

Adverse events will also be summarized by maximum severity. If a subject has an adverse event with unknown severity, then the subject will be counted in the severity category of "unknown," even if the subject has another occurrence of the same event with a severity present. The only exception is if the subject has another occurrence of the same adverse event with the most extreme severity – ("Life-threatening"). In this case, the subject will be counted under the "Life-threatening" category.

4. Adverse Events by Maximum Relationship

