Serious Infections	Serious AEs in the Infections and Infestations SOC	
Active Tuberculosis	Active Tuberculosis CMQ (code 80000188)	
Opportunistic Infections excluding tuberculosis and herpes zoster	Opportunistic infection excluding tuberculosis and herpes zoster CMQ (code 80000189)	
Injection Site Reactions	Narrow	Injection site reaction CMQ (code 80000019)
Malignancies	Narrow	Malignant tumours (SMQ 20000194)
Non-melanoma Skin Cancer (NMSC)	Broad	Skin malignant tumours (SMQ 20000204) excluding terms identified by the Melanoma CMQ (code 80000119)
Malignant Tumours excluding NMSC	'Malignant Tumours excluding NMSC' is identified by the 'Malignant Tumours' search excluding terms identified by the 'Non-melanoma skin cancer (NMSC)' search.	
Hypersensitivity	Narrow	Hypersensitivity (SMQ 20000214)
Serious hypersensitivity reactions	Narrow	Serious AEs in the Hypersensitivity (SMQ 20000214)
Adjudicated Anaphylactic Reaction*	Adjudicated terms will be identified using SDTM data (e.g., CE and PR domains).	
Hepatic Events	Broad	Hepatic failure, fibrosis and cirrhosis and other liver damage-related conditions (SMQ 20000013)
	Broad	Hepatitis, non-infectious (SMQ 20000010)
	Broad	Cholestasis and jaundice of hepatic origin (SMQ 20000009)
	Broad	Liver related investigations, signs and symptoms (SMQ 20000008)
	Narrow	Liver-related coagulation and bleeding disturbances (SMQ 20000015)

* Events will be identified for adjudication by Anaphylactic Reaction SMQ Broad search as specified in the RISA AAC Charter.

Adverse Event per 100 Patient-Years of Exposure

Adverse events occurring during the analysis period for each population will be presented by event rate per 100 patient-years. These will be presented for any TEAEs, serious adverse events, Areas of Special Interest.

AEs per 100 patient-years of exposure is defined as the number of AEs divided by the total exposure in 100 patient-years. Note that one event per preferred term per day per subject will be counted in the calculation of the number of AEs (i.e., a preferred term will not be counted twice on the same day for the same subject). See the calculation method below.

$$100 \times \frac{\text{Number of TEAEs}}{\text{Total Patient Years}}$$

where total patient years is defined as the sum of the study drug exposure (defined as date of last dose – date of first dose + 140 days (5 half-lives)) of all subjects normalized by 365.25, and rounded to one decimal place.

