11.2.2 SAEs (Including Deaths) and Adverse Events Leading to Study Drug Discontinuation

Deaths and all SAEs will be presented in listing format. In addition, SAEs and AE leading to study drug discontinuation will be summarized by System Organ Class and MedDRA Preferred Term.

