11.6 Safety Subgroup Analysis

For RZB, RZB_NL, Retreatment and UST_RZB Populations, AE overview tables will be provided in the subgroup including subjects from Japan only. This subgroup analysis will only be performed in the final analysis, upon study completion.

In addition, the number and percentage, as well as exposure adjusted event rate of hypersensitivity events and injection site reactions will also be summarized among the ALL_RZB Population (150 mg), by the anti-drug antibody (ADA) status during the analysis period.

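### The SAP's list of events per 100 patient-years omits deaths and AEs leading to discontinuation, for which the protocol promises rates, and no departure is declared

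*SAP*

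**What the plan says.** Protocol 8.1.5, with the same commitment in the synopsis, reads: "Summaries (including percentages and event per 100 patient-years) of SAEs, deaths, AEs leading to discontinuation from the study, and pre-specified AESIs will be provided as" (the sentence ends one word later). Four categories are therefore promised both a percentage and a rate.

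SAP 11.2.1 opens its paragraph on rates in general terms: "Adverse events occurring during the analysis period for each population will be presented by event rate per 100 patient-years". The next sentence sets the scope: "These will be presented for any TEAEs, serious adverse events, Areas of Special Interest".

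Elsewhere the SAP handles the two missing categories as follows.
- The overview in 11.2.1 includes AEs leading to discontinuation of study drug, AEs leading to death, and deaths. Its measure is stated as "The number and percentage of subjects experiencing treatment-emergent adverse events will be summarized for the following adverse event categories".
- SAP 11.2.1 also plans SOC/PT tables for AEs leading to death or to stopping study drug, with separate by-subject listings.
- SAP 11.2.2 states "Deaths and all SAEs will be presented in listing format" and "SAEs and AE leading to study drug discontinuation will be summarized by System Organ Class and MedDRA Preferred Term". It mentions no rate.

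The heading of SAP 14.1, for differences between the protocol and the SAP, has no entry beneath it.

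**The concern.** Long-term safety is the primary objective. The study is single-arm and no statistical test is planned, so the descriptive summaries are the whole safety result. Deaths and AE discontinuations are among the first rows a reader will look for.

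A percentage of subjects ignores how long each subject was observed. Counted follow-up differs by population because some subjects bring feeder-study risankizumab time with them and others start at entry to the extension. It also differs between subjects because some stop early. A rate per 100 PY is the usual way to put such outcomes on a common footing with one another and with other sources, and the protocol chose it.

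The SAP does explain a departure from the protocol elsewhere: 11.3.2 gives a reason for grading laboratory values by NCI CTCAE instead of RCTC. Nothing comparable appears for the two missing rates, so a reader cannot tell a decision from an oversight.

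**Working it through.** The plan states no figure on this point, so the main check is textual. The arithmetic that follows is illustration.

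**1. Commitments side by side**

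| Category | Protocol 8.1.5 and synopsis | Rate per 100 PY in SAP 11.2.1 |
|---|---|---|
| SAEs | percentage and rate | listed |
| Deaths | percentage and rate | not listed |
| AEs leading to discontinuation | percentage and rate | not listed |
| AESIs | percentage and rate | listed, as areas of interest |
| Any TEAE | number and percentage | listed (added by the SAP) |

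Four rates are promised, two are carried over, two are missing and one is added.

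**2. Does other SAP text restore them?** The only other exposure-adjusted rate in the SAP text is in 11.6: "exposure adjusted event rate of hypersensitivity events and injection site reactions will also be summarized among the ALL_RZB Population (150 mg"), by ADA status. The rate shells visible in Appendix A cover adjudicated cardiovascular events, AESIs and hypersensitivity. None covers deaths or AE discontinuations.

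**3. Full follow-up by population.** Inputs are the last target days in the SAP window tables and the 140-day extension in the SAP 11.2.1 definition of patient-years.

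PY = (last target day − 1 + 140) / 365.25

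- RZB, Week 304, day 2129: 2268 / 365.25 = 6.21
- RZB_NL, Week 288, day 2017: 2156 / 365.25 = 5.90
- UST_RZB and FUM_RZB, Week 252, day 1765: 1904 / 365.25 = 5.21

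**4. Effect on percentages.** The documents give no event rates, so a range is assumed. With a constant rate, expected percentage = 1 − exp(−rate × PY).

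| Assumed rate per 100 PY | RZB | UST_RZB / FUM_RZB |
|---|---|---|
| 0.2 | 1.23% | 1.04% |
| 0.5 | 3.06% | 2.57% |
| 1 | 6.02% | 5.08% |
| 2 | 11.68% | 9.90% |

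Before rounding, the ratios run from about 1.19 at the lowest rate to 1.18 at the highest. Identical underlying rates therefore give percentages that differ by 18–19%.

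**5. Where the extra RZB time lies.** It is 304 − 252 = 52 weeks of feeder time, inferred from the windows. Every SAP population requires a dose in M15-997 (SAP 5.0), and premature discontinuation of the feeder study is an exclusion (Protocol 5.2.2). No analysed subject can have died or discontinued in the feeder. The one qualification is that an AE may start in the feeder and lead to discontinuation later.

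Event-free share of the denominator = feeder weeks / (feeder weeks + extension weeks to last dose + 20):
- Risankizumab started at extension entry (UST_RZB, FUM_RZB, adalimumab subjects switching at OLE): 0 / 272 = 0%
- Adalimumab subjects switching at Week 16, dosed to Week 252 (280 − 252 = 28 feeder weeks): 28 / 300 = 9.3%
- RZB, dosed to Week 252: 52 / 324 = 16.0%
- RZB, last dose at extension Week 48: 52 / 120 = 43%

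Steps 4 and 5 rest on the same 324 against 272 weeks and are not two separate effects. If the rate is constant over all counted time, percentages shift as in step 4. If feeder weeks carry no events, percentages of fully followed subjects do not shift for that reason, and a rate over integrated time is lowered instead. For these two outcomes the second description is the closer one. Step 4 therefore shows what unequal counted time can do. It does not forecast these two rows.

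**The case against.** The strongest reply is that the SAP is silent and withdraws nothing. Its introduction says that it elaborates the protocol's methods, the lead-in to the rate paragraph is general, and the full list of outputs is a separate document. The appendix holds only non-standard shells. The rates may well be programmed. That stands as a limit on the claim: a reader might infer that the sponsor has decided against these rates, and the documents do not show that. It does not remove the gap. The sentence after the lead-in names categories, and if any TEAEs covered everything, naming SAEs and areas of interest would be redundant.

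Second, the loss is one of presentation. Counts of deaths and total patient-years will both be available, so a crude rate can be worked out by hand. A reader might infer that percentages are all that remains, but SOC/PT tables and listings are planned as well. This is a fair reason to keep the point modest.

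Third, no between-population test depends on these figures. That is true, but populations will be reported with the same measures and will be compared by eye.

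A reader might also go from step 5 to the claim that the rates are understated by 10–19% (300/272 = 1.10; 324/272 = 1.19), or that only extension time belongs in the denominator. Neither is supported. The factor describes a rate that the SAP does not list, so it cannot measure the omission. Nor is it a bound: it is 1.00 for those starting at extension entry and 120/68 = 1.76 for the early stopper above. An extension-only main denominator would itself depart from the protocol, which integrates preceding-study data (8.1.2) and counts TEAEs from the first risankizumab dose in either study (8.1.5).

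**Conclusion.** The point holds as a mismatch between protocol and SAP. Two of four promised rates are absent from the SAP's explicit list, no other SAP text supplies them, and no departure is declared. This finding rests on the text alone.

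The size is illustrative. Fully followed subjects contribute about 6.2 PY in RZB and 5.2 PY in UST_RZB or FUM_RZB, which moves percentages by about 18–19% at equal rates. That assumes dosing to the last window and one constant rate over all counted time, feeder included. The latter is not realistic for deaths and discontinuations. Unequal follow-up from early stopping within the extension also affects percentages, but the documents give no figures to size it.

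The event-free feeder time is a reason to show a second rate beside the protocol's integrated one. It is not a reason to replace it. The point is worth correcting because the outcomes matter and the correction is nearly free.

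**What to change.** In SAP 11.2.1, add deaths and AEs leading to discontinuation of study drug to the list of events per 100 PY, using the patient-year definition already given there. Protocol 8.1.5 speaks of discontinuation from the study and the SAP of discontinuation of study drug, so state which is meant. If the sponsor prefers not to present these rates, record and justify that in SAP 14.1. The cost is one sentence and two rows in the rate tables, from data already collected.

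Optionally, show for these two outcomes a supplementary rate with patient-years from the first M15-997 dose, labelled as such, with a note that entry required completing the feeder study. This needs a second patient-year definition, including how it treats the cut-off at the start of the 75 mg dose in Japan, so it costs somewhat more than the main change.

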8.1.1 Analysis Populations

Subjects are required to have at least one dose of study drug in Study M15-997 to be included in the following populations.

The following populations are to be used for efficacy analyses:

- RZB Population: consists of subjects who were randomized to risankizumab in Studies 1311.3, 1311.30, 1311.28, 1311.38 (150 mg arm only), and M16-178. This population will be used to evaluate the long-term efficacy of risankizumab with loading dose. For subjects from Japan, data after the first dose of RZB from the preceding studies and prior to the start of 75 mg dose will be used for the analyses.
- RZB_NL Population: consists of subjects who were randomized to placebo in the initial study and continued to risankizumab (without loading dose) in Studies 1311.3, 1311.4, 1311.28, and 1311.38 (150 mg arm only). This population will be used to evaluate the long-term efficacy of risankizumab without initial loading dose. For subjects from Japan, data after the first dose of RZB from the preceding studies and prior to the start of 75 mg dose will be used for the analyses.
- Retreatment Population: consists of subjects who were re-randomized to placebo in Part B of Study 1311.4. This population will be used to evaluate the efficacy of re-treatment after temporary withdrawal. For subjects from Japan, data after the re-treatment and prior to the start of 75 mg dose will be used for the analyses.
- UST_RZB Population: consists of subjects who were randomized to ustekinumab in Studies 1311.3 and 1311.28. This population will be used to assess the efficacy of risankizumab when subjects switch from ustekinumab to risankizumab. For subjects from Japan, data prior to the start of 75 mg dose will be used for the analyses.
- ADA_RZB Population: consists of subjects who were randomized to adalimumab in Study 1311.30. This population will be used to assess the efficacy of risankizumab when subjects switch from adalimumab to risankizumab.
- FUM_RZB Population: consists of subjects who were randomized to FUMADERM in Study M16-178. This population will be used to assess the safety and efficacy of risankizumab when subjects switch from FUMADERM[®] to risankizumab.

- RZB Japan Population: consists of subjects from Japan. This population will be used to assess safety and efficacy during the OLE period, regardless of dosing changes in subjects.

Additional analysis populations may be defined when deemed appropriate.

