The RZB Japan Population consists of subjects from Japan during the visits in the OLE period, regardless of dose. This population will be used to assess safety and efficacy during the OLE period, regardless of dose. The RZB Japan Population will only be analyzed in the final analysis, upon study completion.

All Risankizumab Treated (ALL RZB) Population:

The All Risankizumab Treated Population consists of subjects who received at least one dose of risankizumab in this Study M15-997. This population will be used to provide a comprehensive summary of safety, and will be summarized by risankizumab 150 mg, and by any dose of risankizumab.

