9.0 Study Drug Exposure and Compliance

Study drug exposure (days) will be summarized using the sample size, mean, standard deviation, minimum, median and maximum. Study drug exposure will be summarized as follows:

Risankizumab Exposure (in Days):

The Risankizumab Exposure (total duration during the preceding study and Study M15-997) will be defined as follows:

The Risankizumab Exposure = Last risankizumab dose date – First risankizumab dose date (either in Study M15-997 or preceding study) + 84 days, except:

- The Risankizumab Exposure in the Retreatment Population is defined as: Last risankizumab dose date – First retreatment of risankizumab date (either in Study M15-997 or preceding study) + 84 days
- The Risankizumab Exposure in the ALL_RZB Population among subjects who were re-randomized to placebo during Study 1311.4 Part B is defined as: Last risankizumab dose date during Study 1311.4 Part A – First risankizumab dose date + 84 days + Last risankizumab dose date – First retreatment of risankizumab date + 84 days

In addition, number of subjects who have at least one dose of self-injected study drug during Study M15-997 will also be summarized.

A data cutoff date (September 01, 2017) was applied during the first interim analysis in 2017.

A data cutoff date (November 01, 2021) will be applied during the second interim analysis. The duration of study drug exposure will be defined up to this cutoff date.

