11.2 Analysis of Adverse Events

11.2.1 Treatment-Emergent Adverse Events

Treatment emergent adverse events (TEAEs) are defined as any event with an onset date that is after the first dose of risankizumab and with an onset date within 140 days after the last dose of study drug in the analysis period except:

- **TEAE of Retreatment:** TEAE are defined as any event with an onset date that is after the first dose of retreatment and no more than 140 days after the last dose of study drug, and prior to the start of risankizumab 75 mg (if any, for subjects in Japan).
- **TEAE of ALL_RZB (any dose):** TEAEs are defined as any event with an onset date after the first dose of risankizumab through 140 days after the last dose of risankizumab, except for AEs with an onset date during protocol-designed treatment gaps (i.e., placebo period in subjects re-randomized to placebo during Study 1311.4 Part B) that was more than 140 days from the last dose of previous risankizumab treatment and before the first dose of retreatment in the ALL_RZB Population.
- **TEAE of RZB, RZB_NL, UST_RZB, ADA_RZB, FUM_RZB and ALL_RZB (150 mg):** TEAEs are defined as any event with an onset date after the first dose of risankizumab 150 mg through 140 days after the last dose of risankizumab 150 mg, and prior to the start of risankizumab 75 mg (if any, for subjects in Japan), except for AEs with an onset date during protocol-designed treatment gaps (i.e., placebo period in subjects re-randomized to placebo during Study 1311.4 Part B) that was more than 140 days from the last dose of

previous risankizumab 150 mg treatment and before the first dose of retreatment in the ALL_RZB Population.

Events where the onset date is the same as the study drug start date are assumed to be treatment emergent, unless the adverse event start time is prior to the study drug start time. If an incomplete onset date is collected for an adverse event, the event will be assumed to be treatment-emergent unless there is other evidence that confirms that the event is not treatment-emergent (e.g., the event end date is prior to the study drug start date).

The number and percent of subjects experiencing treatment-emergent TEAEs will be tabulated using the Medical Dictionary for Drug Regulatory Activities (MedDRA[®]) system organ class and preferred term.

Summary tables will be presented as follows:

1. Adverse Event Overview

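### RZB Japan is an OLE-period population, but the SAP counts its exposure from the first risankizumab dose in the preceding study and gives its event rates no start date of their own

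*SAP*

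**What the plan says.** **Population.** SAP 5.1: "The RZB Japan Population consists of subjects from Japan during the visits in the OLE period, regardless of dose". Protocol 8.1.1 gives the same purpose: "This population will be used to assess safety and efficacy during the OLE period, regardless of dosing changes in subjects".

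**Exposure.** SAP 9.0 covers both studies: "The Risankizumab Exposure (total duration during the preceding study and Study M15-997) will be defined as follows". The formula is the last risankizumab dose date minus the "First risankizumab dose date (either in Study M15-997 or preceding study) + 84 days, except", followed by two exceptions. One is for the Retreatment Population. The other is for subjects in ALL_RZB who were re-randomized to placebo in Study 1311.4 Part B. RZB Japan is in neither.

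**Rate numerator.** SAP 11.2.1: "Adverse events occurring during the analysis period for each population will be presented by event rate per 100 patient-years". The analysis period is not defined for RZB Japan. The default rule reads "Treatment emergent adverse events (TEAEs) are defined as any event with an onset date that is after the first dose of risankizumab". Three exceptions follow: Retreatment; ALL_RZB at any dose; and RZB, RZB_NL, UST_RZB, ADA_RZB, FUM_RZB and ALL_RZB at 150 mg. RZB Japan is not named, so the default applies to it.

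**Rate denominator.** SAP 11.2.1: "where total patient years is defined as the sum of the study drug exposure", which is in turn "defined as date of last dose – date of first dose + 140 days (5 half-lives". No study or period is attached to the first dose.

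**Visit windows.** SAP Table 10 sets Day 1 for RZB Japan at entry to Study M15-997. SAP 6.0 counts Rx days from the first risankizumab dose in the corresponding study period.

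**The concern.** A population restricted to one period needs its events and its time at risk restricted to that period. For RZB Japan the SAP restricts the membership and the visit windows. It does not restrict the exposure, and it leaves both parts of the event rate open.

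Many Japanese subjects will have had risankizumab before the OLE. SAP 5.1 has clauses for Japanese subjects in the RZB and RZB_NL populations, and protocol 5.6.4 mentions 56 subjects on 75 mg in the Japanese Study 1311.38. Where the clock starts therefore changes the result.

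At stake is the summary that pools Japanese OLE safety whatever the dose, in a trial whose primary objective is long-term safety. Two programmers following the SAP could produce different patient-years from the same data, and one of the possible combinations understates the rates.

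**Working it through.** The documents state no RZB Japan rate, patient-year total or subject count, so there is no figure to reproduce. The check is person-time arithmetic per subject.

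**Inputs**
- Last OLE dose at Week 252 (protocol synopsis): 252 × 7 = 1764 days.
- Follow-on time in the rate: 140 days (SAP 11.2.1). In the exposure summary: 84 days (SAP 9.0).
- Lead-in on risankizumab before the OLE, derived from the last visit windows: Table 1 (RZB) 304 − 252 = 52 weeks = 364 days; Table 3 (RZB_NL) 288 − 252 = 36 weeks = 252 days; Table 10 (for example, ustekinumab switchers) 252 − 252 = 0.
- Possible gap before OLE entry: up to 8 weeks = 56 days (protocol 5.1).

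**Exposure summary, SAP 9.0**
- OLE only: 1764 + 84 = 1848 days.
- As written: 1848 + 364 = 2212 days (52 weeks) or 1848 + 252 = 2100 days (36 weeks).

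**Patient-years for a subject dosed to Week 252**
- From OLE entry: 1764 + 140 = 1904 days; 1904/365.25 = 5.21.
- From first risankizumab dose, 52 weeks: 2268 days = 6.21.
- From first risankizumab dose, 36 weeks: 2156 days = 5.90.

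**Four ways to combine numerator and denominator**

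| Events from | Time from | Result |
|---|---|---|
| OLE entry | OLE entry | Valid OLE rate |
| OLE entry | First risankizumab dose | Too low |
| First risankizumab dose | First risankizumab dose | No dilution, but not an OLE rate |
| First risankizumab dose | OLE entry | Too high |

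**Second row: shortfall = 1 − OLE days / full days**
- Week 252, 52 weeks: 1 − 1904/2268 = 16.0%. With the 8-week gap added: 1 − 1904/2324 = 18.1%.
- Week 252, 36 weeks: 1 − 1904/2156 = 11.7%.
- Last dose at Week 156, 52 weeks: 1 − 1232/1596 = 22.8%.
- Last dose at Week 48, 52 weeks: 1 − 476/840 = 43.3%.
- No lead-in: 0%.
- Illustrative pool of Week 252 subjects, half with 52 weeks and half with none: 1 − 1904/2086 = 8.7%.

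**Fourth row, assuming a constant event rate:** 2268/1904 = 1.191, so 19.1% too high (52 weeks); 2156/1904 = 1.132, so 13.2% too high (36 weeks).

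**A further problem when time starts at the first risankizumab dose.** The corrections for the placebo gap in Study 1311.4 Part B cover only Retreatment and ALL_RZB. SAP 5.1 allows for Japanese subjects in the Retreatment Population. In RZB Japan their withdrawal time would count as time on risankizumab.

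**The case against.** The strongest counter-argument is that the SAP already implies an OLE start. Table 10 puts Day 1 for this population at M15-997 entry, although its note refers only to the first dose date of risankizumab. Read the same way in 11.2.1, the unqualified first dose and the population's analysis period would both begin at OLE entry, and the rate would be right. Moreover, the words that reach back to the preceding study appear only in SAP 9.0, which is a separate summary with 84 rather than 140 added days.

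If the first dose is instead read as the feeder dose, consistency suggests reading the default event rule the same way. SAP 6.0 also uses the baseline before the first risankizumab dose in either study for safety in all populations. Numerator and denominator then match, and nothing is diluted.

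Much of this stands. A reader might infer that RZB Japan rates will be too low. The documents do not support that as a fact, because it needs an OLE reading of the numerator together with a feeder reading of the denominator, and the SAP commits to neither.

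Two things remain. Table 10 governs visit windows, not rates or exposure. And SAP 9.0 is explicit: its exposure for RZB Japan includes feeder time, which contradicts the population definition whatever 11.2.1 means.

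**Conclusion.** The point holds as a conflict in SAP 9.0 and an undefined start in SAP 11.2.1. It does not hold as a demonstrated downward bias. Followed literally, SAP 9.0 gives RZB Japan an exposure that is not OLE-only. No reading of the rate that starts time at the first-ever risankizumab dose gives a valid OLE rate: it is either diluted or mixed with feeder-study data.

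The 12% to 16% shortfall applies only if OLE events are divided by time from the first risankizumab dose, and only to subjects dosed to Week 252 with a 36- to 52-week lead-in. Those lead-ins are derived from the RZB and RZB_NL window tables; other arms may differ. The 43.3% figure is for a single early stopper and would carry little weight in pooled patient-years. The pooled effect cannot be computed because the Japanese arm mix is not given.

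Severity is minor to moderate. The summary is descriptive, country-specific and produced only at the final analysis. The comprehensive safety summary in ALL_RZB is not affected by this point.

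**What to change.** Three additions to the SAP:
- **Section 9.0:** an RZB Japan exception, with exposure = last risankizumab dose date − first risankizumab dose date in M15-997 + 84 days.
- **Section 11.2.1, patient-years:** for RZB Japan, the same start date, with + 140 days.
- **Section 11.2.1, treatment-emergent events:** an RZB Japan bullet, with onset on or after the first M15-997 dose and through 140 days after the last dose, regardless of dose, keeping the existing rule for events on the day of dosing.

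Events and patient-years then cover the same OLE period, and the 1311.4 placebo gap falls outside it. The cost is a few lines of text and one start-date parameter in the programs. No interim RZB Japan output has to be redone, because SAP 5.1 reserves this population for the final analysis.
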